## APPENDIX 2 GUIDELINES FOR PHOSPHORUS AND CALCIUM

The following guidelines summarize the requirements for each parameter during the study.

Parameter	Value	Age Range (Years)	Action
Phosphate	<4.0mg/dL (1.29mmol/L)	12 to <18	Monitor phosphate levels carefully and consider reducing the binder dose by 25% depending on the rate at which phosphate is falling.
	<4.5mg/dL (1.45mmol/L)	10 to <12	
Phosphate	<3.5mg/dL (1.13mmol/L)	12 to <18	Binder should be stopped and phosphate levels monitored closely. The binder should be resumed at 50% of the prior dose when phosphate levels are >4.0mg/dL (1.29mmol/L).
Phosphate	<4.0mg/dL (1.29mmol/L)	10 to <12	Binder should be stopped and phosphate levels monitored closely. The binder should be resumed at 50% of the prior dose when phosphate levels are >4.5mg/dL (1.45mmol/L).
Phosphate	>10.0mg/dL (3.23mmol/L) except during washout periods	10 to <18	Discontinue subject.
Calcium	<8.8mg/dL (2.20mmol/L)	10 to <18	Subject should receive therapy to increase calcium levels.
Calcium	>10.2mg/dL (2.54mmol/L) during Part 2 Treatment Period 1	10 to <18	Active vitamin D sterols should be decreased by 50%, calcium carbonate decreased by 25% and the subjects should be monitored. If after 2 weeks hypercalcaemia persists, active vitamin D sterols should be stopped. If after another 2 weeks it persists the subject should be withdrawn from Part 2 and may continue to Part 3.
Calcium	>10.2mg/dL	10 to <18	Active vitamin D sterols

Parameter	Value	Age Range (Years)	Action
	(2.54mmol/L) during lanthanum carbonate treatment		should be decreased by 50%, calcium carbonate decreased by 25% and the subjects should be monitored. If after 2 weeks hypercalcaemia persists, active vitamin D sterols should be stopped.
Calcium	>11.5mg/dL (2.88mmol/L) during first treatment period of Part 2	10 to <18	Discontinue subject from Part 2, and proceed to Part 3.

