#### 5.2 Concomitant Treatment

Concomitant treatment taken between the dates of the first and last dose of investigational product, inclusive, must be listed on the appropriate CRF page.

Treatments not listed in [Table 4](#) above are considered allowable.

Subjects who require treatment with Vitamin D analogues should maintain a stable dose throughout the study unless modification is required due to hypercalcaemia as specified in Section 6.2.1. Vitamin D therapy including dose, unit, route, regimen, indication and dates of use, and the calcium concentration of the dialysate will also be recorded in the CRF.

Treatment with cinacalcet hydrochloride, or with compounds containing phosphate or magnesium, aluminum, or calcium that are used as a phosphate binder are prohibited during the study.

Contraceptives for females should be taken at least 4 weeks prior to enrollment and continued throughout the duration of the study and for 30 days following the last dose of investigational product.

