### **Hypercalcemia**

If hypercalcaemia (serum calcium >10.2mg/dL (2.54mmol/L) develops during administration of calcium carbonate in Part 2a (Treatment Period 1) of the study, active vitamin D sterols should be decreased by 50%, the dose of calcium carbonate should be decreased by 25%, and the subject should be monitored. If after 2 weeks hypercalcemia persists, active vitamin D sterols should be stopped. If after another 2 weeks from onset of hypercalcemia it persists, the subject should be withdrawn from Part 2a. If the Investigator believes there are no contraindications and the subject is willing to continue, the subject can start Part 3.

If hypercalcemia (serum calcium >10.2mg/dL (2.54mmol/L) develops during administration of lanthanum carbonate, active vitamin D sterols should be decreased by 50%. If after 2 weeks hypercalcemia persists, active vitamin D sterols should be stopped until required.

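### For hypercalcaemia during lanthanum treatment, Appendix 2 lists a calcium carbonate reduction that Section 6.2.1 does not contain

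*Protocol*

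**What the plan says.** Protocol Appendix 2 introduces its table with "The following guidelines summarize the requirements for each parameter during the study". Two rows concern calcium above 10.2 mg/dL in subjects aged 10 to under 18. The first covers Part 2 Treatment Period 1, when calcium carbonate is the study drug. The second covers "2.54mmol/L) during lanthanum carbonate treatment". In both rows active vitamin D sterols are to be reduced by 50%, with "calcium carbonate decreased by 25% and the subjects should be monitored".

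The Hypercalcemia text of Protocol Section 6.2.1 treats the two situations in separate paragraphs. For hypercalcaemia during calcium carbonate in Part 2a it states that "the dose of calcium carbonate should be decreased by 25%, and the subject should be monitored". The lanthanum paragraph says that if hypercalcaemia "develops during administration of lanthanum carbonate, active vitamin D sterols should be decreased by 50" per cent. If it persists after 2 weeks the sterols are to be stopped until they are needed again. That paragraph has no calcium carbonate step and no monitoring step.

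Protocol Section 5.2 adds that compounds containing, among others, "calcium that are used as a phosphate binder are prohibited during the study".

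**The concern.** The first steps of the lanthanum row match those of the calcium-period row, including a dose change to a product that is not the study drug during lanthanum treatment. A site that looks up the table and a site that reads the dosing section will find different instructions for the same laboratory value in the same treatment period.

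This matters more under Version 6.0 than it did before. All new subjects enter Part 2b and receive lanthanum only, so of the two rows for calcium above 10.2 mg/dL only the lanthanum row can apply to them. What is at stake is consistent handling of a safety finding in a paediatric dialysis population. It is not the validity of any planned estimate.

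**Working it through.** The point involves no arithmetic. The check compares the two instructions for the same trigger (calcium above 10.2 mg/dL while on lanthanum).

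| Element | Appendix 2, lanthanum row | Section 6.2.1, lanthanum paragraph |
|---|---|---|
| Active vitamin D sterols, first step | Reduce by 50% | Reduce by 50% |
| Calcium carbonate | Reduce by 25% | Not mentioned |
| Monitoring | Stated | Not mentioned |
| Sterols if hypercalcaemia persists after 2 weeks | Stop | Stop, until needed again |

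The vitamin D reduction and the 2-week stop agree. Three elements differ: the calcium carbonate step, the monitoring step, and the qualifier on how long sterols stay stopped.

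1. **Which row is at fault.** The words "calcium carbonate decreased by 25% and the subjects should be monitored" occur in both Appendix 2 rows. In the Treatment Period 1 row they agree with Section 6.2.1, which has the 25% reduction for that period. Only the lanthanum row disagrees.

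2. **Whether there is study calcium carbonate to reduce.** There is none. Section 3.3 confines calcium carbonate to Part 2a and states that Part 2b gives lanthanum only. For Part 2a subjects, Section 7.1.2.3 has investigational product collected at Visit 2.4, and Section 7.1.2.4 has calcium carbonate stopped for the washout before lanthanum.

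3. **Whether other calcium could be meant.** It could. The Hypocalcemia text of Section 6.2.1 allows therapy to raise calcium in Parts 2 and 3, taken away from meals or at bedtime, with no agent named. A subject on lanthanum might therefore be taking calcium carbonate for that purpose. The Appendix 2 row does not say that it refers to this use, and the lanthanum paragraph of Section 6.2.1 has no corresponding step.

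4. **Whether one text governs.** Section 4.4.1 sends sites to Appendix 2 for phosphorus and calcium levels. The Hypophosphatemia text of Section 6.2.1 sends them there for phosphate and calcium management. Section 5.2 instead points to Section 6.2.1 for vitamin D changes in hypercalcaemia. Each route is live, and the protocol gives no order of precedence.

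5. **Whether this is superseded text.** It is not. Appendix 2 and Section 6.2.1 are both current Version 6.0 text, outside the amendment log.

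**The case against.** The strongest defence is that the extra step does little harm. The row tells sites to reduce calcium carbonate; it does not tell anyone to start or continue it. If the subject takes none, there is nothing to reduce, and what remains matches Section 6.2.1 apart from monitoring and the qualifier on stopping sterols. If the subject takes calcium for hypocalcaemia, the step could be deliberate. This stands as a limit on the practical consequence. It does not remove the mismatch: if the step was deliberate, Section 6.2.1 is incomplete, and if it was carried over from the row above, Appendix 2 is in error.

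A reader might infer more than the documents support:

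- **That the row contradicts the ban on calcium binders.** Section 5.2 bars calcium compounds only when used as a phosphate binder. The row does not describe the calcium carbonate as a binder, and the hypocalcaemia provision leaves room for other use. The tension is indirect.
- **That concurrent calcium carbonate would confound the phosphate endpoint.** This would require a site to read a reduction in a hypercalcaemic child as permission to use a calcium binder. Nothing in the documents shows that.
- **That such subjects would have to be removed.** The Section 4.4.1 criterion concerns a non-study binder taken in place of the investigational product. Use alongside lanthanum does not clearly meet it, and non-binder calcium does not meet it at all.
- **That the SAP is affected.** SAP Section 21.1 cites Protocol Appendix 2 only for hypophosphataemia. It never uses the hypercalcaemia row.

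**Conclusion.** The point holds as a minor internal inconsistency, wrong as written. For calcium above 10.2 mg/dL during lanthanum treatment, Appendix 2 and Section 6.2.1 give different action lists, and sites are directed to both.

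The row covers every such event in Part 2a Treatment Period 2, Part 2b and Part 3. The calcium carbonate step has practical effect only for a subject who is also taking calcium carbonate. The documents give neither the frequency of hypercalcaemia on lanthanum nor the number of subjects likely to be taking calcium for another reason, so no count can be attached. No effect on sample size, analysis sets or the primary calculation is claimed.

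The conclusion rests on reading both texts as operative, which the cross-references support. It takes no position on which clinical instruction is correct.

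**What to change.** The sponsor should reconcile the lanthanum-period hypercalcaemia row of Appendix 2 with the lanthanum paragraph of Section 6.2.1, and check the result against Section 5.2, so that they state one action. The same edit should settle the two smaller differences, namely the monitoring step and the qualifier on stopping sterols. If a calcium carbonate step is intended, both places should say which use of calcium it refers to. The choice of action is the sponsor's clinical decision.

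The cost is one table row, with a matching sentence in Section 6.2.1 if needed, in an amendment. No SAP change follows.

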## ABBREVIATIONS

AE	adverse event
ALP	alkaline phosphatase
ALT	alanine aminotransferase
AST	aspartate aminotransferase
AUC 0-t	area under the plasma concentration-time curve from time zero to the time of the last quantifiable concentration
CC	calcium carbonate
CKD	chronic kidney disease
C max	maximum plasma concentration
ECG	electrocardiogram
eCRF	electronic case report form
EOS	end of study
FAS	Full Analysis Set
FGF-23	fibroblast growth factor 23
GGT	gamma glutamyl transferase
IP	investigational product
KDOQI	Kidney Disease Outcomes Quality Initiative
LC	lanthanum carbonate
MCH	mean corpuscular haemoglobin
MCHC	mean corpuscular haemoglobin concentration
MCV	mean corpuscular volume
PK	pharmacokinetic
PP	per-protocol
PTH	parathyroid hormone
SAE	serious adverse event
SOC	system organ class
SAP	statistical analysis plan
TEAE	treatment-emergent adverse event
TRAP	tartrate-resistant acid phosphatase
WHO	World Health Organisation

## **1. INTRODUCTION**

This statistical analysis plan (SAP) provides a technical and detailed elaboration of the statistical analyses of efficacy, safety, and pharmacokinetic data as described in the final study protocol version 6.0 dated 18 Oct 2016 incorporating most recent amendment #5. Specifications for tables, figures, and listings are contained in a separate document.

## 2. STUDY DESIGN

### 2.1 General Study Design

This study has been approved by the Paediatric Committee of the European Medicines Agency as part of the Paediatric Investigational Plan for lanthanum carbonate. Pharmacokinetic (PK) data will be collected during the study as there are currently no data on lanthanum carbonate in paediatric subjects under the age of 18 years. The data from this study will be evaluated against historical systemic exposure data in adults, in a separate document. The pharmacokinetic assessment is combined with the efficacy and safety sections to reduce the number of studies to be performed and to ease subject enrolment.

#### Part 1: Single-dose, pharmacokinetic assessment

This part of the study was a single-dose pharmacokinetic assessment of lanthanum carbonate in at least 8 subjects. There was a 2-week screening period during which eligibility was determined for Part 1. Subjects who were eligible to participate entered a washout period of up to 3 weeks if the phosphorus level was not above Kidney Disease Outcomes Quality Initiative (KDOQI) required levels. During the washout period the existing phosphate binder treatment was discontinued until phosphate levels had risen above 6.0mg/dL (1.94mmol/L) in subjects aged under 12 years or >5.5mg/dL (1.78mmol/L) in subjects aged over 12 years. At the end of the washout period, subjects were assessed for inclusion in the study based on their serum phosphorus levels.

Subjects participating in Part 1 could begin Part 2a immediately following the completion of the pharmacokinetic assessments. Subjects not participating in Part 1 entered Part 2a after screening at Visit 2/Week 0 (see [Table 1: Schedule of Assessments for Part 1, Part 2a \(Treatment Periods 1 and 2\), and Part 3](#)).

Part 1 is complete and an interim clinical study report interpreting and summarizing the data for the first 10 subjects in Part 1 is available.

#### Part 2a: Open-label, active comparator crossover period

Originally, the design of Part 2 of Study SPD405-207 was a crossover non-inferiority one to allow a formal comparison of the efficacy of lanthanum carbonate with calcium carbonate. It was a single sequence design (8 weeks of calcium carbonate followed by 8 weeks of lanthanum carbonate) to minimize disruption to the subjects. The comparator calcium carbonate was selected to meet the comparator criteria outlined by Paediatric Committee of the European Medicines Agency. Since the originally proposed study included only 1 sequence (calcium carbonate for the 1st treatment period and lanthanum carbonate for the 2nd treatment period) blinding was not applicable, thus the study was open-label. As shown in the study schematic in [Figure 1: Study Design Flow Chart- Part 1, Part 2a \(Treatment Periods 1 and 2\) and Part 3](#) [Figure 1](#), all subjects were to receive lanthanum carbonate in part 2, period 2 of the crossover and had the option to continue on to Part 3 of the study on the same treatment, ie, lanthanum carbonate for up to 6 months. If needed, there was a washout period for up to 3 weeks between treatment with calcium carbonate (Part 2, Treatment Period 1) and lanthanum carbonate

(Part 2, Treatment Period 2). Subjects who discontinued calcium carbonate treatment period/Treatment Period 1 due to hypercalcemia in Part 2 of the originally proposed study could also continue to Part 3 to receive lanthanum carbonate treatment (see Protocol Version 6.0 (Amendment 5), Section 4.5.1 [Subject Stopping Criteria] and Section 6.2.1 [Dosing, Hypercalcemia]) for up to 6 additional months.

Following Version 6.0 (Amendment 5), Part 2 is amended to enrol subjects to receive lanthanum carbonate treatment only. The calcium carbonate treatment followed by lanthanum carbonate treatment is referred to as Part 2a in protocol Version 6 (Amendment 5). Subjects to be enrolled under Version 6 (Amendment 5), of protocol will enter/be enrolled directly into Part 2b, which is 8 weeks of lanthanum treatment only.

#### Part 2b: 8-week lanthanum carbonate treatment

[figure not shown]
Given the extreme difficulty in recruiting enough subjects to obtain the originally proposed sample size of 50 subjects required for the Per-protocol Set for a cross-over non-inferiority study, the active comparator (calcium carbonate) treatment arm was removed (see Part 2a) in Part 2b; serious consideration had to be given to adjust the sample size and focus of the study to safety, in order to complete it. The sample size has been adjusted to include at least 32 subjects who will complete 8 weeks of treatment with lanthanum carbonate and will be assessable for the primary endpoint. As shown in the study schematic in [Figure 2](#) eligible subjects will be enrolled in Part 2b after screening at Visit 1/Week 0 (see [Table 3](#)) to receive 8 weeks of lanthanum carbonate treatment only under Version 6.0 of the protocol. Subjects in Part 2b will have the option to continue on to Part 3 of the study on the same treatment for up to 6 additional months.

#### Part 3: 6-month lanthanum carbonate treatment

Subjects in Part 2a (including subjects in Treatment Period 1/calcium carbonate treatment arm who discontinued due to hypercalcemia; see Protocol Version 6.0 (Amendment 5), Section 4.5.1 [Subject Stopping Criteria] and Section 6.2.1 [Dosing, Hypercalcemia]) and Part 2b may continue to receive open-label lanthanum carbonate for up to 6 additional months of therapy.

The doses selected for Part 1 of the study were those that were suggested for use in children in clinical practice and those in Part 2 are based on known phosphate binder values for maintaining phosphate level balance.

**Figure 1: Study Design Flow Chart- Part 1, Part 2a (Treatment Periods 1 and 2) and Part 3**

[figure not shown]

\* Screening is only required once, either at Part 1 for subjects participating, otherwise at Part 2.

\*\* The washout is only required if phosphorus is below KDOQI guidelines.

Note: The schematic in [Figure 1](#) is applicable to the originally proposed open-label cross over study design.

**Figure 2: Study Design Flow Chart- Part 2b and Part 3 (Protocol Version 6, Amendment 5)**

\*Eligible subjects will enter Part 2b to receive 8 weeks of lanthanum carbonate treatment only under Version 6.0 of the protocol. Screening will occur at Visit 1, Week 0. The washout (W1) is only required if phosphorus is below KDOQI guidelines.

## 2.2 Randomization

Not applicable. This is an open-label study.

## 2.3 Blinding

This is an open-label study; the study includes only 1 sequence in Part 2, (calcium carbonate for the treatment period 1 and lanthanum carbonate for the treatment period 2). Blinding is not applicable.

## 2.4 Schedule of Assessments

[Table 1](#) below presents a schematic of the study design.

### STUDY SCHEDULE(S)

**Table 1: Schedule of Assessments for Part 1, Part 2a (Treatment Periods 1 and 2), and Part 3**

	Part 1 Subjects who enrol into Part 1 will omit the first washout in Part 2 (Visit window ±3 days)			Part 2a (Visit window ±3 days)								Part 3 (Visit window ±1 week)		
Visit	1.0	Washout W1 j	1.1 a	2.0 b	Washout W1 j	2.1	2.2-2.3	2.4	Washout W2 j	2.5-2.7	2.8	3.0-3.4	3.5/End of Study c	Safety Follow-up call k
Week	-5	-4 to -1	-4 to -1	0	0-3 weeks duration	2 d	4, 6 d	8 d	0-3 week duration	10, 12, 14 d	16 d	20, 24, 28, 32, 36	40 d	41-42 d
Informed consent	✓			✓										
In/exclusion criteria	✓			✓	✓ j									
Medical and renal history	✓			✓										
Demographics	✓			✓										
12-lead ECG	✓			✓							✓		✓	
Physical examination	✓		✓	✓									✓	
Vital signs, height and weight	✓		✓	✓				✓			✓		✓	
Local laboratory tests f		✓		✓	✓	✓	✓		✓	✓		✓		
Central laboratory phosphate		✓			✓				✓					

Table 1: Schedule of Assessments for Part 1, Part 2a (Treatment Periods 1 and 2), and Part 3														
	Part 1 Subjects who enrol into Part 1 will omit the first washout in Part 2 (Visit window $\pm 3$ days)			Part 2a (Visit window $\pm 3$ days)								Part 3 (Visit window $\pm 1$ week)		
Visit	1.0	Washout W1j	1.1a	2.0b	Washout W1j	2.1	2.2-2.3	2.4	Washout W2j	2.5-2.7	2.8	3.0-3.4	3.5/End of Studyc	Safety Follow-up callk
Week	-5	-4 to -1	-4 to -1	0	0-3 weeks duration	2 d	4, 6 d	8 d	0-3 week duration	10, 12, 14 d	16 d	20, 24, 28, 32, 36	40 d	41-42 d
Dialysis adequacy	✓			✓		✓	✓	✓		✓	✓	✓	✓	
Confirmation of dietary advice	✓			✓		✓	✓	✓		✓	✓	✓	✓	

a Visit 1.1 should be scheduled for the day after dialysis. See [Table 2](#) for a detailed schedule of assessments.

b For subjects who have completed Part 1, laboratory and other assessments can be completed from Visit 1.0, no further blood samples are required. A consent form to participate in Part 2a must be signed.

c Assessments scheduled for Visit 3.5 should also be carried out at the time of discontinuation for all subjects who withdraw from the study early or as close as possible to the time of discontinuation. These assessments are not required for subjects post-transplantation, however a safety follow-up call is required.

d Visit weeks may be variable depending on duration of washout (+3 weeks).

e Investigational product will be dispensed at Visit 2.0 if eligible, however if a washout is required then investigational product will be dispensed at visit W1.

f Local laboratory assessments for phosphorus, serum calcium, and calcium phosphorus product in Parts 1 and 2 are for titration purposes, as required, and will not be analyzed; data from Visits 3.0-3.4 will be collected and assessed.

g Visit 2.6 only; Each subject will have at least 2 samples taken for pharmacokinetic assessment. These should be taken during defined time windows (to be selected from: 0-2 hours, 2-4 hours and 4-6 hours, after the first dose/meal of the day). Note: If the sampling is not done at Visit 2.6, blood sampling for pharmacokinetics must be taken at an alternative visit during Part 2.

h Visit 3.3 only; Each subject will have at least 2 samples taken for pharmacokinetic assessment. These should be taken during defined time windows (to be selected from: 0-2 hours, 2-4 hours and 4-6 hours, after the first dose/meal of the day). Note: If the sampling is not done at Visit 3.3, blood sampling for pharmacokinetics must be taken at an alternative visit during Part 3.

Table 1: Schedule of Assessments for Part 1, Part 2a (Treatment Periods 1 and 2), and Part 3														
	Part 1 Subjects who enrol into Part 1 will omit the first washout in Part 2 (Visit window $\pm 3$ days)			Part 2a (Visit window $\pm 3$ days)								Part 3 (Visit window $\pm 1$ week)		
Visit	1.0	Washout W1j	1.1a	2.0b	Washout W1j	2.1	2.2-2.3	2.4	Washout W2j	2.5-2.7	2.8	3.0-3.4	3.5/End of Studyc	Safety Follow-up callk
Week	-5	-4 to -1	-4 to -1	0	0-3 weeks duration	2 d	4, 6 d	8 d	0-3 week duration	10, 12, 14 d	16 d	20, 24, 28, 32, 36	40 d	41-42 d

i For subjects entering Part 3 only.

j Only for subjects completing the washout.

k Safety follow-up call to be made 7-14 days following last dose of investigational product. For subjects discontinued due to kidney transplantation, the safety follow up call to be made  $30 \pm 7$  days from the last dose.

Table 2: Detailed Schedule of Assessments for Visit 1.1 in Part 1									
Hour (in relation to dosing time)	Pre-dose	0	3	5	6	8	12	24	48
Physical examination									✓ a
Vital signs (blood pressure and pulse) b	✓							✓	✓ a
Lanthanum carbonate single dose		✓							
Pharmacokinetic blood sampling c	✓		✓	✓	✓	✓	✓	✓	✓
Record adverse events	✓	✓	✓	✓	✓	✓	✓	✓	✓
Record concomitant medications	✓	✓	✓	✓	✓	✓	✓	✓	✓

a An attempt to perform these assessments and procedures should be made for any subject who withdraws or is removed early from the study, as well as those subjects completing the 48 hour period

b Vital signs will be taken within 15 minutes of nominal dosing time.

c The samples should be drawn within  $\pm 5$  minutes of the nominal in the first 4 hours after taking the investigational product,  $\pm 15$  minutes up to 24 hours after taking the investigational product and within  $\pm 60$  minutes thereafter.

Table 3: Schedule of Assessments for Part 2b and Part 3							
	Part 2b (Visit window ±3 days)				Part 3 (Visit window ±1 week)		
Visit	1.0a	Washout W1b	2.1-2.3	2.4	3.0-3.4	3.5/End of Studyc	Safety Follow-up callf
Week	0	0-3 weeks duration	2, 4, 6d	8d	12, 16, 20, 24, 28	32d	33-34d
Informed consent	✓						
In/exclusion criteria	✓	✓ b					
Medical and renal history	✓						
Demographics	✓						
12-lead ECG	✓			✓		✓	
Physical examination	✓					✓	
Vital signs, height and weight	✓			✓		✓	
Local laboratory tests e	✓	✓	✓		✓		
Central laboratory phosphate confirmation		✓					
Biochemistry	✓			✓		✓	
Hematology	✓					✓	

Table 3: Schedule of Assessments for Part 2b and Part 3							
	Part 2b (Visit window ±3 days)				Part 3 (Visit window ±1 week)		
Visit	1.0a	Washout W1b	2.1-2.3	2.4	3.0-3.4	3.5/End of Studyc	Safety Follow-up calli
Week	0	0-3 weeks duration	2, 4, 6d	8d	12, 16, 20, 24, 28	32d	33-34d
Biochemical bone markers	✓			✓		✓	
Pregnancy test (where applicable)	✓					✓	
Lanthanum pharmacokinetics		☐	✓ f		✓ g		
Investigational product dispensed	✓ h	✓ h	✓	✓ i	✓		
Investigational product collected			✓	✓	✓	✓	
Dose adjustment (as needed) and compliance			✓	✓	✓	✓	
Record adverse events	✓	✓	✓	✓	✓	✓	✓
Record concomitant medication	✓	✓	✓	✓	✓	✓	✓
Dialysis adequacy	✓		✓	✓	✓	✓	
Confirmation of dietary advice	✓		✓	✓	✓	✓	

Table 3: Schedule of Assessments for Part 2b and Part 3							
	Part 2b (Visit window ±3 days)				Part 3 (Visit window ±1 week)		
Visit	1.0a	Washout W1b	2.1-2.3	2.4	3.0-3.4	3.5/End of Studyc	Safety Follow-up calli
Week	0	0-3 weeks duration	2, 4, 6d	8d	12, 16, 20, 24, 28	32d	33-34d

a A consent form to participate in Part 2b must be signed.

b Only for subjects completing washout.

c Assessments scheduled for Visit 3.5 should also be carried out at the time of discontinuation for all subjects who withdraw from the study early or as close as possible to the time of discontinuation. These assessments are not required for subjects post-transplantation; however a safety follow-up call is required.

d Visit weeks may be variable depending on duration of washout (+3 weeks).

e Local laboratory assessments for phosphorus in Part 2b are for titration purposes, as required, and will not be analyzed; data from Visits 3.0-3.4 will be collected and assessed.

f Visit 2.2 only; Each subject will have at least 2 samples taken for pharmacokinetic assessment. These should be taken during defined time windows (to be selected from: 0-2 hours, 2-4 hours and 4-6 hours, after the first dose/meal of the day). Note: If the sampling is not done at Visit 2.2, blood sampling for pharmacokinetics must be taken at an alternative visit during Part 2b.

g Visit 3.3 only; Each subject will have at least 2 samples taken for pharmacokinetic assessment. These should be taken during defined time windows (to be selected from: 0-2 hours, 2-4 hours and 4-6 hours, after the first dose/meal of the day). Note: If the sampling is not done at Visit 3.3, blood sampling for pharmacokinetics must be taken at an alternative visit during Part 3.

h Investigational product will be dispensed at Visit 1.0 if eligible, however if a washout is required then investigational product will be dispensed at visit W1.

i For subjects entering Part 3 only.

j Safety follow-up call to be made 7-14 days following last dose of investigational product. For subjects discontinued due to kidney transplantation, the safety follow up call to be made 30 ± 7 days from the last dose.

